Title of the Study: CCRC: Randomized trial of L-arginine in severe asthma patients grouped by exhaled nitric oxide levels (NCT #01841281)

Principal Investigator: [name], MAS

Updated: December 15, 2019

Last IRB Approval Date: July 16, 2018

PROTOCOL

PURPOSE AND PROCEDURES:

1. Describe the study format (pilot, phase I, phase II, or III) and whether it is single or multi-center; industry-sponsored or investigator initiated; and the funding source.

This is an investigator-initiated, early phase II study funded by NHLBI.

2. Describe the specific aims of the study, research methods and procedures.

We hypothesize that a subset of adult severe asthma patients will respond to supplemental L-arginine and derive clinical benefit from the addition of this therapy to standard-of-care medications. We hypothesize that these patients will have lower exhaled NO concentrations (<20 ppb) than -non-responders. The aim is:

1. To test the hypothesis that adult severe asthma subjects with exhaled breath NO concentrations <20 ppb will have fewer American Thoracic Society (ATS)-defined asthma exacerbations over 3 months when treated with L-arginine compared to subjects with FeNO > 25.

The major impact of this study will be to identify the adult severe asthma cohort that will benefit from supplemental L-arginine therapy to define the underlying mechanisms of arginine benefit in asthma. This follows our initial 20 subject trial of L-arginine in asthma subjects ([name] et al., Pharmaceuticals 2011) that was designed to determine how L-arginine was metabolized (by testing serum markers) and whether certain participants had clinical benefit.

To do this, we will recruit a total of 50 ATS-defined asthmatic subjects with ≥ 2 asthma exacerbations in past two months and enroll them in a randomized, blinded, placebo-controlled, cross-over designed trial of L-arginine and placebo. We will compare 25 subjects with -low FeNO <20 with 25 subjects that have -high FeNO > 25 ppb.

Study Design:

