- *Exhaled Breath Condensate (EBC) Collection:* Collections of EBC from each participant will occur immediately after collection of the exhaled breath samples. Participants will breathe into a chilled collection tube for 10 minutes as recommended in the 2005 ATS/ERS statement. Collection tubes will be purchased from Respiratory Research (Charlottesville, VA), a commercial entity that has received FDA approval for measuring EBC pH in subjects with cough. Immediately after collection, the tubes will be frozen on dry ice for transport to [name] lab. Total time of sample collection should be 10 minutes. Breath samples will undergo chemical analysis at [name] laboratory. Volatiles in breath samples will be concentrated using Solid Phase Microextraction (SPME). Analyte compounds will then be loaded on a chromatographic column for a nominal pre-separation and will be detected with a differential mobility spectrometer, according to protocols previously developed in [name] lab.
- *Blood draw* 16 cc of blood will be drawn at each visit. Serum will be collected for cytokine profiling and NOx measurements and L-arginine metabolites. Whole blood will be processed for genotyping.

- *Office Spirometry will be performed with portable office spirometer (Spriolab II).*
- *Physical examination and symptom questionnaire*

Brief Study outline: 1 screening visit and 4 study visits

- Screening Visit
- Explanation of protocol
 - Informed consent
 - History and physical examination
 - Two exhaled NO measurements (to determine if subjects > or < 25 ppb)
- Study Day 1
- History and physical examination (brief) to verify stable clinical status
 - Blood collection #1
 - Spirometry #1
 - Exhaled NO measurement #1
 - Sputum collection #1
-
- Respiratory symptom questionnaire #1
 - Start symptom and peak flow diary
 - Start oral L-arginine or placebo
- Study Day 80
- Updated clinical history
 - Blood collection #2
 - Spirometry #2
 - Exhaled NO measurement #2
 - Sputum collection #2
 - Respiratory symptom questionnaire #2
- Study Day 110
- Updated clinical history
 - Blood collection #3
 - Spirometry #3
 - Exhaled NO measurement #3
 - Sputum collection #3
 - Respiratory symptom questionnaire #3
- Study Day 190
- History and full physical examination
 - Blood collection #4
 - Spirometry #4
 - Exhaled NO measurement #4
 - Sputum collection #4
 - Respiratory symptom questionnaire #4
 - Stop oral L-arginine or placebo

5. If blood samples will be collected, identify in what manner:

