The primary endpoint was the total number of "moderate" exacerbations during the 12-week interventional period, as defined by recent the ATS/ERS 2009 statement [2]. A moderate asthma exacerbation is defined as any of the following: 1) a drop in am PEF>30% from baseline on two consecutive days, 2) need for initiation of oral steroids or an increased dose of inhaled corticoid steroid on any two consecutive days, 3) doubling of short-acting β -agonist use (e.g. number of puffs of albuterol)/ day for 2 consecutive days [3-5]. The secondary clinical endpoints were recorded at each of the six study visits, these included: 1) asthma control test score, 2) FEV1 (liters), 3) FVC (liters), 4) FEV1/FVC (%), and 5) Weight. The secondary biological endpoints including FeNO and untargeted metabolites.

Metabolites measurement

Longitudinal plasma metabolite levels were measured by hydrophilic interaction liquid chromatography (HILIC) in both positive and negative modes and gas chromatography (GC) mode. The peak intensity was measured for the compounds and were annotated to specific known metabolites. Relative standard deviation (RSD) for each compound found in more than one mode in quality control samples were calculated and the intensities of compound with lowest RSD was chosen for the downstream analysis.

Clinical trial analysis

For the sample size calculation, we used a conservative power estimate based on t-test analysis of 2x2 cross-over design [6]. For a sample size of 50 people, we would have 95% power to detect a 0.6 standard deviation change in the mean lung function at $\alpha = 0.025$ and accounting for 10% attrition rate. Improvements of this magnitude are consistent with those reported in recent crossover trials in asthma with either FEV1 [7], symptoms scores [8], or AM PEF [9] as outcomes. Statistical analyses for the clinical trials were performed using SAS University Edition (SAS Institute Inc., Cary, NC, USA.) and R (public access). Data were analyzed on an intention-to-treat basis and the significant level was defined by p value less than 0.05. A generalized linear mixed model was used for analysis accounting for correlated repeated measurements which enable us to account for expected missing data points [10]. This model considered differences in baseline levels of function, by allowing for person-specific random effects (random intercepts). The distribution of exacerbation events was assumed to be a Poisson distribution. For

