the primary hypothesis, we included an indicator in the model that allows for the subjects to be on active treatment. We first examined the carryover and period effect then tested for the treatment effect and examined the interaction term between treatment and FeNO. For secondary clinical outcomes, we performed the same analysis except we used linear mixed effect for the continuous endpoints.

Identify baseline metabolites as predictors for treatment response

We further defined the treatment response by reducing exacerbation events by 33% during L-arginine treatment. The individual event reduction was calculated by (events during treatment period minus events during placebo period)/events during placebo period. Subjects with zero event at baseline or did not complete both treatment and placebo phase were excluded. The baseline metabolomic profiling (first visit) was used for the downstream analysis. Partial Least Square-Discriminant analysis (PLS-DA) and hierarchical cluster analysis (using Euclidean as similarity measure and Ward's linkage as clustering algorithm) were performed using MetaboAnalyst 4.0 [11]. to identify the predictive metabolites. Clinical characteristics were compared between treatment response versus non-response groups using t-test (continuous characteristics) or Fisher's exact test (categorical characteristics with small sample sizes).

Longitudinal metabolomic profiling analysis

A linear mixed model was used to test the association between the longitudinal metabolite intensities and the clinical outcomes including FeNO at each visit. Metabolites pattern change between two biological conditions including 1) treatment vs. placebo, 2) high vs. low FeNO groups during treatment period, 3) treatment response vs. non-response groups during treatment period were tested using the method of multivariate empirical Bayes (MEBA) time-series analysis [12] built in the MetaboAnalyst 4.0. Hotelling-T2 statistics were used to rank the metabolites with different temporal profiles between two biological conditions under the study.

References

- [name], Last M., Bratt J.M., Kwan V.W., O'Roark E., Linderholm A. L-Arginine Supplementation and Metabolism in Asthma. *Pharmaceuticals* 2011, 4, 187-201.

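### The plan gives no signed L-arginine versus placebo estimate for any metabolite, and its FeNO-group metabolite comparison has no placebo reference; a cross-over model for a few named analytes would supply both

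*Combined protocol and SAP*

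**What the plan says.** The protocol's item on aims has one numbered aim, about exacerbations. It also gives as part of the study's impact "to define the underlying mechanisms of arginine benefit in asthma". Under Study visits 1-4, the blood-draw entry reads: "Serum will be collected for cytokine profiling and NOx measurements and L-arginine metabolites". The Investigational Drug section explains the low dose by the risk that high doses raise ADMA, which it describes as a NOS inhibitor.

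In the SAP, Outcomes lists five secondary clinical endpoints and then, separately: "The secondary biological endpoints including FeNO and untargeted metabolites". NOx and ADMA are not named there.

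Clinical trial analysis describes the cross-over model for exacerbations: "We first examined the carryover and period effect then tested for the treatment effect and examined the interaction term between treatment and FeNO". It then extends that model: "For secondary clinical outcomes, we performed the same analysis except we used linear mixed effect for the continuous endpoints". Biological endpoints are not mentioned in that extension.

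Besides a baseline analysis to predict response, metabolites receive two analyses under Longitudinal metabolomic profiling analysis:

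- A linear mixed model relating "the longitudinal metabolite intensities and the clinical outcomes including FeNO at each visit", with no treatment term stated.
- MEBA comparisons of "1) treatment vs. placebo, 2) high vs. low FeNO groups during treatment period", and of responders with non-responders, also during the treatment period. Pattern changes are tested by MEBA, and "Hotelling-T2 statistics were used to rank the metabolites with different temporal profiles between two biological conditions under the study".

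**The concern.** Two things are missing from the metabolite plan.

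**Direction and size.** Hotelling's T2 is a quadratic form, so a rise and an equal fall score the same. For the arginine pathway the direction is what matters. Higher L-arginine with stable ADMA would fit the proposed benefit. Higher ADMA would point the other way and bears on the protocol's reason for the dose.

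**A placebo reference.** FeNO groups are selected, not randomised. A metabolite that always differs between them can rank high in treatment-period samples with no L-arginine effect, and could then be read as a different response to the drug. The same applies to responders versus non-responders. The placebo-period samples that would cancel a standing difference are collected but are not used in these two comparisons.

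What is at stake is the mechanistic reading of the trial, not its primary result.

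**Working it through.** **Inputs from the SAP (Clinical trial analysis).** 50 people and 10% attrition, so 50 x 0.9 = 45 completers. I take FeNO groups of 22 and 23.

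**Inputs assumed, because the documents give none.** Correlation r between visits of 0.5 to 0.7; standing group difference d of 0.3, 0.5 or 0.8 between-person SD; SD of the within-person log difference of 0.20 or 0.30.

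**The plan's own figure.** For a 2x2 cross-over t-test with 45 completers, 0.6 SD of the within-person difference and two-sided alpha 0.025, the noncentrality is 0.6 x sqrt(45) = 4.02 on 43 df. Power is 95.2%, which agrees with the stated 95%. Nothing below depends on this except the 45 completers.

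**1. Direction.** With mean difference vector m and covariance S, T2 = n m' S^-1 m. Replacing m by -m leaves it unchanged. One simulated set of 45 differences gave T2 = 16.83, and 16.83 again with every sign reversed.

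The cross-over contrast keeps the sign. Its 95% half-width is 2.017/sqrt(45) = 0.301 SD of the within-person log difference. For true ratios of 1.10 and 1/1.10 = 0.91 (log values +0.0953 and -0.0953):

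| SD of log difference | Ratio 1.10 | Ratio 0.91 | T2 noncentrality, 45 x (0.0953/SD)^2 |
|---|---|---|---|
| 0.20 | 1.04 to 1.17 | 0.86 to 0.97 | 10.2 in both directions |
| 0.30 | 1.01 to 1.20 | 0.83 to 0.99 | 4.5 in both directions |

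**2. High versus low FeNO, treatment period only, no drug effect.** I use a classical two-sample T2 on k = 2 visits, uncentred, with a 5% cut-off.

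- Noncentrality = (22 x 23/45) x d^2 x k/(1 + (k-1)r).
- F = T2 x (45-k-1)/(k x 43) on k and 45-k-1 df, here 2 and 42.
- Example, d = 0.5 and r = 0.5: 11.24 x 0.25 x 2/1.5 = 3.75, giving 36.8%.

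| d | r = 0.5 | r = 0.7 |
|---|---|---|
| 0.3 | 15.6% | 14.2% |
| 0.5 | 36.8% | 32.9% |
| 0.8 | 76.7% | 71.0% |

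A 20,000-run simulation agreed at d = 0.5 (36.8% and 33.5%). In the same runs, at d = 0.5 and 0.8, the period-adjusted cross-over treatment-by-FeNO contrast rejected 4.9-5.2% of the time, because a person's standing level cancels in the within-person difference.

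**3. Which terms the replacement model needs.** The SAP's description names the treatment-by-FeNO interaction but not a FeNO main effect. If that main effect is left out of a random-intercept model, the standing difference leaks into the interaction.

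- With known variance and balanced periods, the bias is d(1-r) and the standard error is sqrt((1-r^2)(1/22 + 1/23)).
- At d = 0.5, r = 0.5: 0.25/0.258 = 0.97, a two-sided 5% rejection rate of about 16%. At r = 0.7: 0.15/0.213 = 0.70, about 11%.
- At d = 0.8: about 34% (0.40/0.258 = 1.55) and 20% (0.24/0.213 = 1.13).
- In simulation, adding the main effect brought the rate back to about 5%.

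**4. Limits of the replacement.** The difference in response between FeNO groups has a 95% half-width of 2.020 x sqrt(1/22 + 1/23) = 0.60 SD of the within-person log difference. Four independent, unadjusted null contrasts give 1 - 0.95^4 = 19% chance that at least one interval excludes a ratio of 1.

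**The case against.** The strongest reply is that the SAP calls these metabolites untargeted and applies a discovery tool to them. The one aim is exacerbations, and mechanism appears only as an impact statement. Nothing promises a targeted estimate for L-arginine, ADMA or NOx. That stands, and it is why this is an optional improvement and not a fault in a promised analysis.

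Four stronger readings are tempting, and the documents do not support them:

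- **That metabolites are only ranked.** The SAP says pattern changes were tested as well. A test still gives no direction, size or interval.
- **That T2 is why NOx and ADMA go unestimated.** NOx appears only in the protocol's blood-draw entry and has no stated analysis of any kind. ADMA is never named as an assay or endpoint; it matters here only if the panel annotates it.
- **That 33-37% is an error rate of this plan.** The SAP states no T2 cut-off, and classical T2 stands in for the empirical Bayes version. The SAP speaks of temporal profiles; if these were centred at the start of the period, a standing difference would cancel, though ordinary change over the 12 weeks would not. No centring is stated either way.
- **That FeNO is left without an analysis.** The SAP's wording groups FeNO with the clinical outcomes, so it plausibly receives the cross-over model already and needs only to be named.

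Two further replies carry some weight. The SAP is written in the past tense, so the added analysis may have to be post hoc. By-group precision is also low. Neither removes the value of a signed overall estimate.

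**Conclusion.** The point holds as a low-cost, exploratory improvement, worth considering but not essential. No stated analysis yields a signed L-arginine/placebo effect for any metabolite. The FeNO-group and response-group comparisons cannot isolate a different response to L-arginine unless profiles are centred. With 45 completers, an overall ratio of 1.10 could be reported as 1.04 to 1.17 at an assumed log-difference SD of 0.20, so a usable estimate is within reach of data the protocol already collects. How far the FeNO comparison could mislead depends on the assumed standing difference, correlation and uncentred T2, so those rates are illustrative. A reader might infer that the trial's main conclusion is weakened. It is not: the primary test and the treatment-by-FeNO test on exacerbations use the cross-over model and are untouched.

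**What to change.** Keep MEBA for untargeted discovery. Under Longitudinal metabolomic profiling analysis, add:

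- **Analytes:** L-arginine, ADMA if annotated, NOx if assayed. State that FeNO, as a secondary biological endpoint, gets the same model.
- **Data:** log value at the last sample of each treatment period (Days 80 and 190 in the protocol's visit outline). The SAP refers to six visits, so say which ones these are. Peak-intensity ratios suffice if only untargeted data exist.
- **Model:** the SAP's cross-over linear mixed model with period, treatment, FeNO-group main effect, treatment-by-FeNO interaction and person random intercept, with the carryover check the SAP already uses. The main effect must be written out.
- **Report:** L-arginine/placebo ratios with 95% confidence intervals, overall and by FeNO group, labelled exploratory and unadjusted for multiplicity. For any analyte without data, state that it was not assayed or annotated.
- **Responders versus non-responders:** reference it to placebo-period samples as well, or state that it does not isolate an L-arginine effect.

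The cost is SAP wording and up to four models of an existing form, with no new samples. The drawbacks are the roughly 19% chance of at least one false exclusion of 1 across four independent nulls, and the wide interval for the between-group difference. If the data are already unblinded, label the analysis post hoc.
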